All children in the FluSNIFF-toddler trial will receive the nasal flu vaccine. At the start, 1500 children aged 12 to 23 months will be given the nasal spray influenza vaccine (Fluenz), and 1500 children will receive nasal spray of a placebo. We will then compare how many children in each group were brought to see a doctor who diagnosed wheezing in their chest in the following four weeks. Then, four weeks later, the children will return for their second study visit. If they had LAIV at the first visit, children will

receive the placebo, and if they originally received the placebo children will then receive LAIV. We will again compare rate of wheezing in each group over the following four weeks.

The children's parents will not know whether their child received the vaccine or the placebo, so that this does not influence how likely they will be to visit their doctor.

If there are similar amounts of wheezing detected by doctors in children who have had the LAIV vaccine or the placebo, then then the UK may be able to offer the vaccine to children aged one year and over in the future. As for all vaccines, this decision will be made for the NHS by the Government's Joint Committee of Vaccination and Immunisation.

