#### 15 Statistics

#### 15.1 Sample size

The primary objective of this study is to determine the relative risk of medially attended wheezing in 28 days following LAIV vaccination compared with placebo. The null and alternate hypotheses are:

H0: Proportion of wheezing LAIV = Proportion of wheezing Placebo

H1: Proportion of wheezing LAIV ≠ Proportion of wheezing Placebo

Where the proportion of wheezing is calculated as the number of participants with respiratory wheezing diagnosed by a health practitioner requiring medical attention within 28 days following receiving LAIV or a placebo. We chose 28 days as this is the common interval to observe intermediate reactions following vaccination. The study was a cross-over design, i.e. participants randomised to LAIV or placebo at Day0 will receive placebo or LAIV at Day28, respectively. Although there is no data on the ideal washout period, it is biologically reasonable to assume that the impact of LAIV will last shorter than 28 days. The data from a previous publication comparing medically significant wheeze rates between LAIV and inactivated vaccine groups reported 44 vs 20 cases in the first 28 days following vaccination, and 11 vs 14 cases between 29-42 days post-vaccination, further supporting our assumption. Therefore, we will use both Day 0-28 and Day 28-56 periods in the primary analysis in the primary analysis.

The sample size calculation is based on the below assumptions:

- 1. The proportion of medially attended wheezing is 0.9% following placebo in 28 days following vaccination;
- 2. The relative risk of interest is 2;

- 3. Study power of 80%;
- 4. Type I error of 0.05 two-sided;

Based on the above sample size, the study will need to recruit 2800 effective participants. Given the study endpoint will be extracted based on electronic medical records, we expect the attrition rate will be low. The total sample size will be 3000.

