#### 15.2 Description of statistical methods

The primary analysis population will be participants who are randomised and received LAIV or placebo at Day 0 and Day 28. The proportion of participants with a diagnosis of medically attended wheezing between Day 0 to Day 28 and between Day 28 and Day 56, along with the associated 95% confidence intervals will be presented. When calculating the proportion, the numerator will be the number of participants randomised and received LAIV or placebo at the start of each period. The analysis will be conducted according to the vaccine received. The difference in proportions between the two arms will be analysed using Pearson's chi-squared test after combining the data from both periods. The corresponding 95% CI will be derived using a standard method. The risk of wheezing following LAIV will be estimated by a mixed-effects model with the study vaccine received at the start of each period, study period (months) and sequence as fixed effects and participant ID as a random effect to account for within-subject variability. The Kaplan-Meier curve will be used to visualise the time to medically attend wheeze. Participants who withdrew from the study will be censored in the analysis at the time of withdrawal. Non-diagnosed participants will be censored in the analysis at 28 days following vaccination in both periods.

Carryover effects were assessed by testing for the interaction between vaccine and sequence, and if significant, the comparison between the two groups will be done for the two periods separately. We will also test the interaction between the study period (by months) and the vaccine to understand if any increased risk observed following LAIV is affected by the background wheezing risk.

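### The only named test of the primary hypothesis ignores the cross-over pairing, and no analysis is tied to the relative risk that the objective asks for

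*Protocol*

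**What the plan says.** Protocol section 15.1 sets the target: "The primary objective of this study is to determine the relative risk of medially attended wheezing" over 28 days after LAIV compared with placebo. Its null hypothesis is "Proportion of wheezing LAIV = Proportion of wheezing Placebo". It also says that both 28-day periods enter the primary analysis.

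Section 15.2 defines the primary analysis population as children dosed at Day 0 and at Day 28. It then gives two analyses of the product comparison:

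- The difference in proportions is tested by Pearson's "chi-squared test after combining the data from both periods", with a corresponding 95% interval by an unnamed standard method.
- The risk of wheeze after LAIV is estimated by a mixed-effects model with product, study period and sequence as fixed effects and "participant ID as a random effect to account for within-subject variability".

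Neither analysis is labelled primary. No link function or effect measure is given for the model, and the words relative risk do not occur in section 15.2.

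**The concern.** Pearson's test on pooled periods treats the LAIV records and the placebo records as two separate groups of children. Here they are the same children. The variance of a within-child difference contains a covariance term that the pooled test leaves out. If children prone to wheeze tend to wheeze in either period, that covariance is positive and the pooled standard error is too large. Clustering is plausible, because sections 3, 11.1 and 12.1.1 describe enrichment for children with previous wheeze, bronchiolitis or eczema.

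The trial exists to detect a possible harm, so an oversized standard error costs sensitivity where it matters. There is also a gap in reporting. The objective is a relative risk, the interval attached to the named test is for a difference in proportions, and the one analysis that respects the pairing has no stated scale and no stated precedence.

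**Working it through.** **Inputs.** From section 15.1: placebo risk p0 = 0.009 ("The proportion of medially attended wheezing is 0.9% following placebo"); "The relative risk of interest is 2", so p1 = 0.018; 80% power; two-sided 5%; 2800 effective children. Assumption, not in the protocol: within-child correlation ρ between the two periods, taken as 0, 0.05, 0.1 and 0.2.

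**The plan's own figure.** The formula for two independent proportions gives 2580 per product without continuity correction and 2798 with it. The second matches 2800. The sample size therefore also treats the records as independent, with each child counted once under each product.

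**What ρ means here.** P(wheeze in both periods) = p0·p1 + ρ·√[p0(1−p0)·p1(1−p1)] = 0.000162 + ρ × 0.012556. At ρ = 0.1 this is 0.001418. Dividing by 0.009, about 16% of children who wheeze after placebo would also wheeze after LAIV, against 1.8% under independence. At ρ = 0.05 and 0.2 the shares are about 9% and 30%.

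**Type I error.** Under the null both risks are 0.009, and the true variance of the difference is (1−ρ) times the pooled one. The real error rate at a nominal 5% is therefore 2Φ(−1.96/√(1−ρ)): 4.4% at ρ = 0.05, 3.9% at 0.1 and 2.8% at 0.2. Simulation with 2800 children agrees:

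| ρ (assumed) | Type I error, Pearson | Type I error, paired | Power at RR 2, Pearson | Power at RR 2, paired |
|---|---|---|---|---|
| 0 | 4.95% | 4.97% | 84.0% | 84.2% |
| 0.05 | 4.3% | 4.9% | 84.5% | 85.9% |
| 0.1 | 3.8% | 4.9% | 85.2% | 87.6% |
| 0.2 | 2.8% | 5.0% | 86.7% | 91.1% |

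**Interval for the difference at RR 2.** Pooled SE = √[(0.008919 + 0.017676)/2800] = 0.00308, a half-width of 0.60 percentage points around 0.9.

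Paired SE = √[(b + c − d²)/2800], where b and c are the two discordant probabilities and d = 0.009. At ρ = 0.1, b = 0.016582 and c = 0.007582, so SE = 0.00293 and the half-width is 0.57. The pooled interval is about 2%, 5% and 11% too wide at ρ = 0.05, 0.1 and 0.2.

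**Interval for the relative risk at RR 2.** Treating records as independent, SE(log RR) = √[0.991/25.2 + 0.982/50.4] = 0.243, giving 1.24 to 3.22. Paired at ρ = 0.1, SE = √[(b + c)/(2800·p0·p1)] = √[0.024165/0.4536] = 0.231, giving 1.27 to 3.14.

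**Sample size under a paired test.** McNemar's test needs 2583 children at ρ = 0, 2461 at 0.05, 2340 at 0.1 and 2096 at 0.2, all below 2800.

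**The case against.** The best defence is that section 15.2 already deals with pairing. The mixed model carries product, period, sequence and a participant effect, so chi-squared can be read as the simple test of equal proportions and the model as the estimator. Link function and interval method are details that a protocol may leave to its analysis plan. A relative risk can be computed from the two reported proportions. The pooled test errs on the conservative side and exceeds 80% power in every scenario above. The correlations are assumptions, and enrichment makes clustering plausible without fixing its size.

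Most of this stands, and it limits how large the problem is. It does not remove it. The protocol has fixed a test and an interval, and both are wrong for paired data if wheeze clusters. Its own random effect concedes that within-child variability needs handling. Two analyses of one comparison can disagree, and nothing says which one decides. A relative risk computed from pooled proportions would still need an interval that respects the pairing.

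**Conclusion.** The point holds, with modest size. The only named test of the hypothesis, and its interval, assume independence that the design does not have. With positive within-child correlation the result is conservative. Over assumed correlations of 0.05 to 0.2, type I error falls to about 4.3% to 2.8%, and about 1 to 4 points of power are lost against a paired test. Near zero correlation nothing is lost. Separately, and whatever the correlation, the protocol does not say which analysis decides and ties none to the relative risk.

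Some stronger readings are not supported:

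- **Inflated false positives or an undersized trial.** A reader might infer either. Positive correlation moves the error rate down, the planned 2800 reproduces, and a paired analysis needs fewer children.
- **Two declared primary results.** The protocol labels neither analysis primary; what is missing is precedence.
- **A non-significant test will be taken as proof of similarity.** The lay summary does begin a sentence with "If there are similar amounts of wheezing detected by doctors in children who have had the LAIV vaccine or the placebo", but it says only that the UK may then be able to offer the vaccine, and leaves the decision to the national advisory committee. It sets no rule based on a p-value. Treating the relative risk of 2 in the sample size as a non-inferiority margin would add a criterion that the protocol never set.

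**What to change.** In section 15.2, replace the pooled Pearson test as the inferential analysis with one named paired analysis that reports the relative risk and its 95% interval. A suitable choice is a log-link (modified Poisson) GEE with product, period and sequence as covariates and robust variance clustered on child. If a simple test is wanted, use McNemar's test, or Mainland-Gart to allow for period. Keep the pooled proportions and chi-squared as descriptive, and state the role of the mixed model, for example as a sensitivity analysis, with its link and effect measure.

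The cost is a wording change in the protocol and analysis plan, made before unblinding. It needs no additional children, visits or data, and the sample size can stay as it is.

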#### 15.3 Interim analyses

There will no formal interim analysis.

#### 15.4 Missing data

The level and pattern of the missing data in the baseline variables and outcomes will be reported. The potential causes of any missing data will be investigated and documented as far as possible. Any missing data will be dealt with using methods appropriate to the conjectured missing mechanism and level of missing.

## 16 Data Management and quality assurance

The Chief Investigator will be responsible for all data that accrues from the study. The sponsor will act as data controller, University of Oxford will act as a data processor under appropriate agreements.

#### 16.1 Access to Data & Data Protection

Direct access will be granted to authorised representatives from the Sponsor, host institution and the regulatory authorities to permit trial-related monitoring, audits and inspections. The study protocol, documentation, data and all other information generated will be held in strict confidence. No information concerning the study or the data will be released to any unauthorised third party, without prior written approval of the sponsor.

#### 16.2 Data Recording

uMed securely collects clinical, patient-reported, and study data in compliance with GCP and regulatory standards. Data is obtained from the following primary sources:

- EHR Data: Extracted from UK general practices (EMIS and TPP systems)
- ePRO/eDiary/eConsent Data: Captured directly from patients via digital surveys for informed consent, subjective outcomes and other patient reported data as required by the Protocol
- Other Study Data: Collected from sites through digital Case Report Forms (CRFs) for protocolspecific activities

All data is stored and managed within uMed's secure cloud infrastructure on Amazon Web Services (AWS) in the London region (UK). Patient-identifiable data remains within this controlled environment. Data management includes strict governance, access control, audit logging, and filtering for National Data Opt-Out and exclusion criteria. Source data files are retained in their original form for traceability and auditability. Data handling adheres to GDPR and relevant local regulations, with access restricted to authorized personnel.

All participant reported adverse event data will be entered onto electronic diary cards (e-diaries) for a maximum of 28 days following administration of the IMP. The eDiary provides a full audit trial of edits and will be reviewed at time-points as indicated in the schedule of events. Any adverse event continuing beyond the period of the diary will be copied into the eCRF as required for safety review.

The participants will be identified by a unique trial specific number and code in any database. The name and any other identifying detail will NOT be included in any trial data electronic file, with the exception of the electronic diaries, for which consent will be obtained to store the participant email

address for quality control purposes. Only site research staff, sponsor staff, monitors (as delegated by sponsor) and University of Oxford data managers have access to view the email address.

#### 16.3 Record keeping

The Investigators will maintain appropriate medical and research records for this trial, in compliance with GCP and regulatory and institutional requirements for the protection of confidentiality of volunteers. The Investigators will permit authorised representatives of the Sponsor(s) and Host institution, as well as ethical and regulatory agencies to examine (and when required by applicable law, to copy) clinical records for the purposes of quality assurance reviews, audits and evaluation of the study safety and progress.

Identifiable information such as contact details will be stored for a minimum of 25 years from the end of the study. This includes storage of consent forms. Storage of these data will be reviewed every 5 years and files will be confidentially destroyed if storage is no longer required. Considerations at the time of this review will include the value of retaining this information for participant safety (e.g. to inform participants of unexpected safety signals emerging from post-licensing surveillance), as a resource for the participants (e.g. if they wish to check which vaccines they have received in the study) and any regulatory requirements. Financial information will be stored for 7 years. De-identified research data maybe be stored indefinitely. If volunteers consent to be contacted for future research, a record of this consent will be recorded, retained and stored securely and separately from the research data.

#### 16.4 Source Data and Case Report Forms (CRFs)

All protocol-required information will be collected via the uMed Platform. Source documents are the NHS electronic medical records. Source documents are original documents, data, and records from which the participant CRF data are obtained. For this study, these will include, but are not limited to, volunteer consent form, diaries, electronic medical records and correspondence.

To prevent withdrawal of a participant due to relocation, if there is a nearby participating site and with the consent of the participant, copies of relevant participant research records (such as ICF, paper source documents) will be transferred to the local site using secure email addresses such as nhs.net or by password protected sheets. The electronic research data stored by uMed will also be transferred to the new site. The original records will be retained by the recruiting site.

#### 16.5 Data Quality and monitoring

Due to the large volume of electronically collected research data, uMed will adopt a risk-based approach to source data verification. Critical safety and primary endpoint data will undergo complete verification, whereas non-critical data will be selectively verified using random sampling. This approach is aligned with regulatory guidance and ensures efficient, high-quality data monitoring consistent with GCP requirements. This is detailed further in uMed's Data Management Plan.

Data collection tools will undergo appropriate validation to ensure that data are collected accurately and completely. Datasets provided for analysis will be subject to quality control processes to ensure analysed data is a true reflection of the source data.

Trial data will be managed in compliance with uMed and, for study analysis, Oxford Vaccine Group (University of Oxford) data management SOPs. If additional, study specific processes are required, an approved Data Management Plan will be implemented

#### 17 Trial committees

#### 17.1.1 Trial Steering Committee

A Trial Steering Committee will be formed to oversee the study, and advise the Study Management Committee on key issues of study conduct, including, but not limited to, study pauses due to safety concerns on the advice of the DSMB.

#### 17.1.2 Data Safety Monitoring Board

A Data Safety Monitoring Board (DSMB) will be convened. The DSMB will evaluate frequency of events, safety and efficacy data as specified in the DSMB charter. The DSMB will make recommendations concerning the conduct, continuation or modification of the study for safety reasons to the Trial Steering Committee.

The DSMB will review SAEs deemed possibly, probably or definitively related to study interventions. The DSMB will be notified within 24 hours of the CI/Sponsor being aware of their occurrence. The DSMB can recommend placing the study or specific arms of the study on hold if deemed necessary following a study intervention-related SAE.

DSMB formal reviews after 100 and 500 participants and at the end of the trial are detailed in section 14.11.

#### 17.1.3 Study Management Group

The trial management group consists of chief investigators and project manager from the sponsor team, representatives from the Oxford Royal College of GPs viral surveillance network, and representatives from uMed.

#### 18 Protocol Deviations

A trial related deviation is a departure from the ethically approved trial protocol or other trial document or process (e.g. consent process or IMP administration) or from Good Clinical Practice (GCP) or any applicable regulatory requirements. Deviations from the protocol will be documented in a protocol deviation form according to SOP R&D/Gen/Admin/009 and filed in the trial master file.

These will be managed as per Sponsor (UHS) SOP R&D/Gen/Admin/009.

### 19 Serious Breaches

The Medicines for Human Use (Clinical Trials) Regulations contain a requirement for the notification of "serious breaches" to the MHRA within 7 days of the Sponsor becoming aware of the breach.

A serious breach is defined as "A breach of GCP or the trial protocol which is likely to affect to a significant degree —

- (a) the safety or physical or mental integrity of the subjects of the trial; or
- (b) the scientific value of the trial".

In the event that a serious breach is suspected the Sponsor must be contacted within 1 working day. In collaboration with the CI the serious breach will be reviewed by the Sponsor and, if appropriate, the Sponsor will report it to the REC committee, Regulatory authority and the relevant NHS host organisation within seven calendar days.

## 20 Ethical And Regulatory Considerations

#### 20.1 Declaration of Helsinki

The Investigator will ensure that this trial is conducted in accordance with the principles of the Declaration of Helsinki.

#### 20.2 Guidelines for Good Clinical Practice

The Investigator will ensure that this trial is conducted in accordance with relevant regulations and with Good Clinical Practice.

#### 20.3 Approvals

Following Sponsor approval the protocol, informed consent form, participant information sheet and any proposed advertising material will be submitted to an appropriate Research Ethics Committee (REC), HRA (where required), regulatory authorities (MHRA in the UK), and host institution(s) for written approval. No amendments to this protocol will be made without consultation with, and agreement of, the Sponsor.

The Investigator is responsible for ensuring that changes to an approved trial, during the period for which regulatory and ethical committee(s) approval has already been given, are not initiated without regulatory and ethical committee(s)' review and approval except to eliminate apparent immediate hazards to the subject (i.e. as an Urgent Safety Measure).

#### 20.4 Other Ethical Considerations

Study team members are not eligible for participation in the study. Family members of the study team are not barred from inclusion in the trial.

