## 12.4 Blinding and code-breaking

Participants' parents/legal guardians and analysing statisticians will remain blind to treatment allocation. Clinical staff involved in study delivery will be aware of which vaccine the participant is receiving (arm allocation). To maintain blinding as much as possible from attending healthcare providers during the study, arm allocation will be concealed from other healthcare provider contacts via the electronic case report form and will only be visible to site staff at the time data is being entered during a vaccination visit.

If the clinical condition of a child necessitates unblinding to vaccine or placebo allocation, the local investigator will have unrestricted and immediate access to break the treatment code via the participants electronic case report form if they find it is in the best interest of the trial subject. This will be done if unblinding is thought to be relevant and likely to change clinical management.

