#### 12.5.2 Diary reports

Participants' parents/legal guardians will receive a digital diary request at 7 and 14 days after each inperson study visit during the trial, issued via uMed. This will ask them whether their child has attended a healthcare provider since their last visit or diary entry. If they answer yes, they will be directed to further questions regarding the location and nature of this contact with a healthcare provider.

Participants will not be provided with a 24-hour telephone number to contact the study team for medical advice, as this would significantly impact the primary outcome measure which is dependent on the participant's family conducting their normal healthcare seeking behaviour. Participants will be advised to seek their normal routes of healthcare advice via NHS provision of they have any medical concerns regarding their child, whether or not they are considered related to the study. This information will be captured via the digital diary.

Participants will be provided with a 24h telephone number and email address to report hospital admissions to the study.

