## 13.1.3 Blinding of IMPs

As the investigators are unblinded there will be no blinding of IMPs, however specific instructions will be given to sites to ensure the participant's parent/legal guardian are unable to see which of vaccine or placebo is being given to their child. Specific site training will explain how vaccine/placebo should be handled and the positioning of parent/carer and child to avoid unblinding of the parent/carer.

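### Section 20.4 lets staff members' own children enrol without condition, so a parent with access to the allocation is possible, contrary to the parent blinding in 12.4; the likely effect is very small

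*Protocol*

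**What the plan says.** Protocol 20.4 bars study team members themselves and then adds: "Family members of the study team are not barred from inclusion in the trial". It does not define the study team and attaches no condition to the permission. The exclusion and temporary exclusion criteria (11.3, 11.3.1) do not mention relatives of staff.

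On blinding, Protocol 12.4 says: "Participants' parents/legal guardians and analysing statisticians will remain blind to treatment allocation". The same section says: "Clinical staff involved in study delivery will be aware of which vaccine the participant is receiving (arm allocation". Section 13.1.3 adds: "As the investigators are unblinded there will be no blinding of IMPs", and relies on site instructions and training so that the parent cannot see which product is given. As a partial safeguard, 12.4 says that allocation in the eCRF "will only be visible to site staff at the time data is being entered during a vaccination visit". The local investigator can also break the code where the child's clinical condition calls for it.

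On why parents are blinded, the Lay Summary (section 4) says: "so that this does not influence how likely they will be to visit their doctor". Section 12.5.2 describes a "primary outcome measure which is dependent on the participant's family conducting their normal healthcare seeking behaviour", and gives this as the reason for not offering families a 24-hour medical advice line.

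**The concern.** Every participant is a toddler, so barring study team members excludes nobody. The clause that has practical effect is the one that admits their families. The relative who matters is the parent, because the parent decides whether a wheezing child is taken to a doctor. If that parent works in delivery at the child's site, one person is both someone who must be blind and someone who knows the allocation.

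At stake is differential care-seeking in the primary outcome. A parent who knows that the child has had the vaccine under suspicion for wheeze might consult more readily, or might discount the symptoms. In a two-period crossover, a parent who learns the product at Day 0 also knows what will be given at Day 28. A parent who learns it only at Day 28 can change care-seeking in the second period only.

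**Working it through.** **The passages side by side.**

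1. Who may enrol: any family member of the study team who meets the criteria (20.4, 11.2, 11.3). This includes a staff member's own child.
2. Who must be blind: all parents and legal guardians, without exception (12.4).
3. Who knows the allocation: delivery staff (12.4) and investigators (13.1.3).
4. What stands between 1 and 3: the shielding of the parent's view at dosing (13.1.3) and the limit on eCRF visibility (12.4). Neither says what to do when the parent is one of the staff. A parent on the team who does not handle the child's visit has no routine view; a parent who does handle it, or who is told, has one.

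Statements 1 to 3 cannot all hold for a child whose parent is unblinded delivery staff at that child's site, unless sites make an arrangement that the protocol does not describe.

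**The plan's own figure.** Section 15.1 assumes: "The proportion of medially attended wheezing is 0.9% following placebo in 28 days following vaccination". It adds a relative risk of 2, 80% power and two-sided alpha of 0.05, and arrives at 2800 effective participants. With p1 = 0.009, p2 = 0.018 and their mean 0.0135, the pooled two-proportion formula gives

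n0 = [1.960 × √(2 × 0.0135 × 0.9865) + 0.842 × √(0.009 × 0.991 + 0.018 × 0.982)]² / 0.009² = 2580 per condition.

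With continuity correction,

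n = (n0/4) × [1 + √(1 + 4/(n0 × 0.009))]² = 2798.

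This matches 2800, since each crossover child supplies both conditions. The present point does not alter that figure.

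**Size of the effect.** The documents give neither the number of staff children, k, nor the factor m by which a parent's knowledge multiplies attendance after LAIV. Both are assumptions. With a true relative risk of 1, a 0.9% risk per period and 3000 children:

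- expected RR = 1 + (k/3000) × (m − 1)
- change in expected LAIV-period events = k × 0.009 × (m − 1)
- expected placebo-period events = 3000 × 0.009 = 27

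| k | share of 3000 | m | RR | change in events |
|---|---|---|---|---|
| 15 | 0.5% | 1.5 | 1.0025 | +0.07 |
| 30 | 1% | 2 | 1.010 | +0.27 |
| 60 | 2% | 2 | 1.020 | +0.54 |
| 60 | 2% | 0.5 | 0.990 | −0.27 |
| 60 | 2% | 3 | 1.040 | +1.08 |
| 150 | 5% | 3 | 1.100 | +2.70 |

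The row with m = 0.5 represents a parent who discounts symptoms. For the type I error, treat the two conditions as samples of 2800 and divide the induced difference by its standard error. At k = 60 and m = 3, the difference is 0.00936 − 0.009 = 0.00036, the standard error is √(2 × 0.00918 × 0.99082/2800) = 0.00255, and the shift is 0.14. The two-sided error is then 1 − Φ(1.96 − 0.14) + Φ(−1.96 − 0.14), about 0.052. At k = 150 and m = 3 it is about 0.064. Both settings are deliberately extreme.

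**The case against.** The strongest reply is that 12.4 is unconditional. Read with 20.4, it means that a staff member's child may enter but the parent must still be kept blind, for instance by colleagues dosing the child and entering the data. Section 13.1.3 requires training to prevent parent unblinding, 12.2.2 leaves exclusion to the investigator's discretion, and 12.4 restricts eCRF visibility. This is a fair reading, and it limits the point: the protocol does not set out to enrol children with unblinded parents. It does not remove the point, because nothing tells a site to make that arrangement and 20.4 grants the permission without it.

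A reader might infer four stronger things that the documents do not support.

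- **That parent blinding is broken for the trial.** It could fail only for the children concerned, and only where the parent has access.
- **That these children are open-label in both periods.** This needs a parent who learns the allocation at Day 0. The study team is undefined and may include people who cannot see allocation, such as the blinded statisticians, and family members include nieces and nephews whose own parents are blind.
- **That staff relationship is not recorded.** The CRF and pre-screen questions are not shown. One can say only that the protocol makes no provision for recording it.
- **That the bias is systematic and upward.** Its direction is unknown, and opposite reactions may partly cancel.

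**Conclusion.** The inconsistency between 20.4 and 12.4 is real, and it touches the blinding that the protocol itself ties to the primary outcome. It is a minor improvement and no threat to the trial's conclusion. With 15 to 60 affected children and a 1.5- to 2-fold rise in attendance after LAIV, the relative risk under the null moves to between 1.0025 and 1.02, against a relative risk of interest of 2. That is 0.07 to 0.54 of an event beside about 27 expected placebo events. Even 60 children with a threefold rise add only about one event and bring the type I error to about 0.052. All these sizes rest on an assumed number of children and an assumed behavioural effect. The case for acting is that eligibility is fixed in this document, the route to unblinding is avoidable, and closing it costs little.

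**What to change.** Replace the permission in 20.4 with a cross-reference to a new exclusion in 11.3. Suggested wording: children are not eligible if a parent, legal guardian or household member has access to treatment allocation, whether as unblinded delivery staff or through code-break access at the child's site. State that other relatives of staff remain eligible. Tying the rule to access, and not to the delegation log as a whole, avoids excluding families of team members who cannot see allocation.

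Add one question to the digital pre-screen, which section 12.2.1 caps at 15 questions, and confirm the answer at the Day 0 eligibility review so that families using face-to-face consent are covered.

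The cost is a short text change, one pre-screen question and the loss of a few recruits. The sample size is unaffected.
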